5.4.1.1 Screening for hepatitis B

Prior to initiation of Everolimus, the following three categories of patients should be tested for hepatitis B viral load and serologic markers, that is, HBV-DNA, HBsAg, HBs Ab, and HBc Ab:

- All patients who currently live in (or have lived in) Asia, Africa, Central and South America, Eastern Europe, Spain, Portugal and Greece.
[<http://wwwnc.cdc.gov/travel/yellowbook/2012/chapter-3-infectious-diseases-related-to-travel/hepatitis-b.htm>]
- Patients with any of the following risk factors:
 - known or suspected past hepatitis B infection,
 - blood transfusion(s) prior to 1990,
 - current or prior IV drug users,
 - current or prior dialysis,
 - household contact with hepatitis B infected patient(s),
 - current or prior high-risk sexual activity,
 - body piercing or tattoos,
 - mother known to have hepatitis B
 - history suggestive of hepatitis B infection, e.g., dark urine, jaundice, right upper quadrant pain
 - Additional patients at the discretion of the investigator.

The management guidelines, in 5.2.2.3, are provided according to the results of the baseline assessment of viral load and serological markers for hepatitis B.

5.4.1.2 Screening for hepatitis C

Patients with any of the following risk factors for hepatitis C should be tested using quantitative RNA-PCR:

- known or suspected past hepatitis C infection (including patients with past interferon ‘curative’ treatment),
- blood transfusions prior to 1990,
- current or prior IV drug users,
- current or prior dialysis,
- household contact of hepatitis C infected patient(s),
- current or prior high-risk sexual activity,
- body piercing or tattoos

At the discretion of the investigator, additional patients may also be tested for hepatitis C. The management guidelines, in 5.2.2.3, are provided according to the results of the baseline assessment of hepatitis C viral load.

5.4.1.3 Pregnancy and assessments of fertility

There are no adequate data from the use of everolimus and TRC105 in pregnant women. The safety of women of childbearing capacity cannot be implied for the existing data with TRC105. Studies with everolimus in animals have shown reproductive toxicity effects including embryo-toxicity and fetotoxicity. The potential risk for humans is unknown. Everolimus should not be given to pregnant women unless the potential benefit outweighs the potential risk to the fetus. If a pregnancy occurs while on study treatment, the newborn will be followed for at least 12 months. It is not known whether everolimus is excreted in breast milk. However, in animal studies everolimus and/or its metabolites readily passed into the milk of lactating rats. Women taking everolimus should therefore not breast-feed.

Women of childbearing potential

Women of child-bearing potential, defined as all women physiologically capable of becoming pregnant, must use highly effective contraception during the study and for 8 weeks after stopping treatment. Highly effective contraception is defined as either:

- Total abstinence: When this is in line with the preferred and usual lifestyle of the subject. [Periodic abstinence (e.g., calendar, ovulation, symptothermal, post-ovulation methods) and withdrawal are not acceptable methods of contraception]
- Sterilization: have had surgical bilateral oophorectomy (with or without hysterectomy) or tubal ligation at least six weeks before taking study treatment. In case of oophorectomy alone, only when the reproductive status of the woman has been confirmed by follow up hormone level assessment

- Male partner sterilization (with the appropriate post-vasectomy documentation of the absence of sperm in the ejaculate). [For female subjects on the study, the vasectomised male partner should be the sole partner for that subject].
- Use of a combination of any two of the following (a+b or a+c or b+c):
 - a. Use of oral, injected, implanted or other hormonal methods of contraception
 - b. Placement of an intrauterine device (IUD) or intrauterine system (IUS)
 - c. Barrier methods of contraception: Condom or Occlusive cap (diaphragm or cervical/vault caps) with spermicidal foam/gel/film/cream/vaginal suppository
- In case of use of oral contraception, women should have been stable on the oral agent before taking study treatment.

Male Contraception

Sexually active males must use a condom during intercourse while taking the drug and for 8 weeks after stopping treatment and should not father a child in this period. A condom is required to be used also by vasectomized men in order to prevent delivery of the drug via seminal fluid. Female partners of male patients must also be advised to use one of the following contraception methods: Use of (1) oral, injected, implanted or other hormonal methods of contraception, or (2) intrauterine device (IUD) or intrauterine system (IUS), or (3) prior male/female sterilization.

Fertility

The potential for everolimus and TRC105 to cause infertility in male and female patients is unknown. However, menstrual irregularities, secondary amenorrhea and associated luteinizing hormone (LH)/follicle stimulating hormone (FSH) imbalance has been observed with everolimus. Based on non-clinical findings, male and female fertility may be compromised by treatment with everolimus and TRC105.

5.4.2 Treatment Phase

The following evaluations and procedures will be performed during the **treatment phase**: (All assessments should be performed within 5 working days of the protocol-specified date).

- Physical examination, vital signs, weight, and performance status on weeks 4, 8, 12, 16, 20 and 24.
- Laboratory assessments: CBC with differential and platelet count, serum chemistries (glucose, BUN, creatinine, total protein, albumin, bilirubin, calcium, alkaline phosphatase, AST, and ALT), and serum electrolytes (Na, K, Cl) on week 1 and at the beginning of each cycle until week 24.
- Lipid panel (cholesterol, triglycerides, HDL, and LDL) in a fasting state (at least 8 hours) should be obtained at least on cycle 2 and, if elevated, repeated on each cycle until recovery to baseline value or grade 1 (see 5.2.2.2 for management of hyperlipidemia and hyperglycemia).

Serum estradiol levels on weeks 4, 12, and 20 in women receiving goserelin.

- Hepatitis panel as clinically indicated.
- Research biopsy (core needle biopsy of the tumor) at week 4 (required).
- Tumor assessments: Ultrasound of the breast will be obtained on week 4, 8, 12, 16, 20 and 24. Mammogram will be obtained on week 24. Additional PET scans or CT of the chest, abdomen, and pelvis, or bone scans are not required during treatment phase except as clinically indicated (see section **7.2 Measurement of Effect**). MRI breast will be obtained at baseline, week 12 and 24.
- Evaluation of the ejection fraction with an echocardiogram/MUGA only as clinically indicated.
- Surgical evaluation at the end of neoadjuvant therapy. **There must be at least 4 weeks between the last dose of everolimus and TRC105 and surgery.** Patients will continue letrozole until the day before surgery.
- Concomitant medication assessment.
- Assessment of adverse events.

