4.1.1 Definition of a Dose Limiting Toxicity (DLT)

A **dose-limiting toxicity (DLT)** is defined as:

- a) Any grade 3 or 4 non-hematologic toxicity except anorexia, alopecia, nausea (which is not refractory to antiemetics), fatigue, fever without neutropenia;
 - b) Failure to recover to baseline (except alopecia) after delaying the next dose by more than 14 days;
 - c) Grade 3 or 4 neutropenia complicated by fever >38.5°C or infection, or grade 4 neutropenia of ≥7 days duration; or
 - d) Grade 4 thrombocytopenia, or grade 3 thrombocytopenia complicated by hemorrhage.
- In addition, accrual will be halted as a result of any grade ≥3 hemorrhage, cerebrovascular and vasovagal adverse events; FDA will be contacted to discuss further accrual or potential need for protocol amendment.

4.1.2 Dose escalation rule:

Dose escalation will follow the decision rules shown in **table 4-2**.

Table 4-2. Dose escalation rules

Number of Patients with DLT at a Given Dose Level	Escalation Decision Rule
0 out of 3	Enter 3 patients at the next dose level.
1 out of 3	Enter 3 additional patients in the same dose level (for a total of 6 patients at this dose level). If 0 of the 3 additional patients experience DLT, then proceed to the next dose level. If 1 or more of these additional patients experience DLT (i.e., ≥ 2 of 6 total patients), dose escalation will be

	stopped.
≥ 2 out 3	Dose escalation will be stopped.
If MTD not reached	Cohort 2 will be selected for RP2D

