5.2.2.2 Management of Hyperlipidemia and Hyperglycemia

Treatment of hyperlipidemia should take into account the pre-treatment status and dietary habits. Blood tests to monitor hyperlipidemia must be taken in the fasting state. Grade 2 or higher hypercholesterolemia (>300 mg/dL or 7.75 mmol/L) or grade 2 hypertriglyceridemia or higher (>2.5x upper normal limit) should be treated with a 3-hydroxy-3-methyl-glutaryl (HMG)-CoA reductase inhibitor (e.g. atorvastatin, pravastatin, fluvastatin) or appropriate triglyceride-lowering medication, in addition to diet. Note: Concomitant therapy with fibrates and an HMG-CoA reductase inhibitor is associated with an increased risk of a rare but serious skeletal muscle toxicity manifested by rhabdomyolysis, markedly elevated creatine phosphokinase (CPK) levels and myoglobinuria, acute renal failure and sometimes death. The risk versus benefit of using this therapy should be determined for individual patients based on their risk of cardiovascular complications of hyperlipidemia.

Dyslipidemia (including hypercholesterolemia and hypertriglyceridemia) has been reported in patients taking everolimus. Monitoring of blood cholesterol and triglycerides prior to the start of everolimus therapy and periodically thereafter as well as management with appropriate medical therapy is recommended. Hyperglycemia has been reported in patients taking everolimus. Monitoring of fasting serum glucose is recommended prior to the start of Everolimus and periodically thereafter. More frequent monitoring is recommended when everolimus is co-administered with other drugs that may induce hyperglycemia. Optimal glycemic control should be achieved before starting a patient on Everolimus. Hyperlipidemia and hypertriglyceridemia should be treated according to local best clinical practice (**Table 5-5**). Patients should be monitored clinically and through serum biochemistry for the development of rhabdomyolysis and other adverse events as required in the product label/data sheets for HMG-CoA reductase inhibitors (statins).

Table 5-5. Management of hyperlipidemia/hypertriglycemia associated with everolimus

Severity	Everolimus Dose Adjustment and Management Recommendations
Grade 1	No dose adjustment required. Initiate appropriate medical therapy and monitor.
Grade 2	No dose adjustment required. Manage with appropriate medical therapy and monitor.

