5.4 Study Procedures

5.4.1 Screening phase

Informed consent will be obtained before study-specific screening evaluations are performed. Screening evaluations must be performed within 4 weeks prior to day 0. Results of tests or examinations done as standard of care prior to obtaining informed consent and within 56 days prior to day 0 may be used rather than repeating tests.

The following evaluations and procedures will be performed during the screening phase:

- Signed informed consent.
- Clinical evaluations: medical history, demographics, weight and height, complete physical examination, vital signs and performance status.
- Determination of the surgical procedure to be performed at the time of diagnosis without the neoadjuvant treatment by the surgical oncologist in the multidisciplinary team. Determinations include unresectable (for locally advanced disease that cannot be adequately resected unless tumor shrinkage is achieved), mastectomy, and lumpectomy.
- Laboratory assessment: UA, CBC with differential and platelet count, serum chemistries (glucose, BUN, creatinine, total protein, albumin, bilirubin, calcium, alkaline phosphatase, AST, and ALT), serum electrolytes (Na, K, Cl), ferritin, and a lipid panel (cholesterol, triglycerides, HDL, and LDL) in a fasting state (at least 8 hours).
- Determination of menopausal status: FSH, LH, and estradiol levels.
- Pregnancy test in women with childbearing potential.
- Research biopsy (core needle biopsy of the tumor) (required).
- Sentinel lymph node biopsy if required.

- Estrogen and Progesterone receptor status.
- Her-2-neu by immunohistochemistry and or FISH (Negative: IHC 0, 1 or 2+ or non-amplified by FISH).
- Tumor assessments: Mammogram and breast ultrasound are required. PET/CT scan or CT scan of chest, abdomen, pelvis, with bone scan will be obtained. If the scan shows disease outside the breast and/or the axilla, the patient will not be enrolled in the trial.
- 12-lead EKG. Evaluation of the ejection fraction with an echocardiogram or MUGA, if clinically indicated.
- Concomitant medication assessment.
- Patients who have satisfied basic eligibility criteria will be assigned with a study patient number and the patient can proceed to be consented.
- Hepatitis B and C panels (see 5.2.2.3, table 5-2 and table 5-4 for Hepatitis B and C interpretation).

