5.4.3 Safety Follow-up Phase

Patients will complete participation in the protocol at the time of surgery and will not be followed unless the patient requires follow up of adverse events. The following evaluations and procedures will be performed at **early termination**. Every effort should be undertaken for the following procedures to be completed within 10 days.

- Clinical evaluations: Weight, physical examination (complete), vital signs and performance status. There must be a complete and clear documentation of objective response or disease progression using the RECIST criteria. Reason(s) for discontinuation must be documented.
- Laboratory assessment: UA, CBC with differential and platelet count, serum chemistries (glucose, BUN, creatinine, total protein, albumin, bilirubin, calcium, alkaline phosphatase, AST, and ALT), serum electrolytes (Na, K, Cl), and lipid panel (cholesterol, triglycerides, HDL, and LDL) in a fasting state (at least 8 hours).
- Tumor assessments: Mammogram, breast ultrasound, and breast MRI. Spiral CT scans of chest, abdomen, and pelvis, bone scan, and any other procedure are not required per protocol but will be obtained if clinically indicated.
- Concomitant medication assessment.
- Assessment of adverse events. If the patient has an ongoing toxicity, the patient should be followed until resolution or stabilization. Serious and non-serious adverse events occurring

within 30 days of day 0 of the last treatment should be reported on the appropriate adverse event CRF.

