7.2.1 Antitumor Effect

Response and progression will be evaluated in this study using the new international criteria proposed by the Response Evaluation Criteria in Solid Tumors (RECIST)¹¹⁸ Committee (http://ctep.cancer.gov/protocolDevelopment/docs/recist_guideline.pdf)¹¹⁸. Changes in only the largest diameter (one-dimensional measurement) of the tumor lesions are used in the RECIST criteria.

Table 7-1: Study Calendar (see 5.4 Study Procedures)

	SC	Treatment Phase ^{11, 13}												End of treatment ⁷	Follow up	
		C1D1	C1D4	C1D15	C2D1	C2D15	C3D1	C3D15	C4D1	C4D15	C5D1	C5D15	C6D1			C6D15
Informed consent	X															
Demographics	X															
Inclusion/Exclusion	X															
Past Medical History	X															
History Present Illness	X															
Concurrent Medications		X-----X														
Prior therapy	X															
Physician Visits	X	X			X		X		X		X		X		X	X
Physical Examination	X	X			X		X		X		X		X		X	X
Performance status	X	X			X		X		X		X		X		X	X
Vital Signs	X	X			X		X		X		X		X		X	X
Height/Weight	X	X			X		X		X		X		X		X	X
CBC and differential	X		X		X		X		X		X		X		X	X
Chemistries/Electrolytes	X		X		X		X		X		X		X		X	X
FSH, LH,estradiol levels	X															
Estradiol levels ¹⁵					X				X				X			
Pregnancy test ¹⁴	X															
Lipid panel ¹	X				X											
Hepatitis panel ²	X															
Urinalysis ³	X															
12-lead EKG	X															
Serum ferritin level	X															
Everolimus serum level		X ¹⁰			X ¹⁰											
TRC105 serum level		X ¹⁰			X ¹⁰											
Anti-TRC105 antibodies (APA) ¹¹		X			X		X		X		X		X			X ¹¹
VEGF-A serum ¹²	X			X	X											X
sEng / TGF-β serum ¹²	X			X	X											X
Angiopoietin-1/2 serum ¹²	X			X	X											X
Research Biopsy ⁴	X				X											X
Adverse Events		X-----X														

Mammography	X														X	
Breast ultrasound	X				X		X		X		X		X		X	
Breast MRI ⁵	X								X						X	
Body CT/MRI/PET ⁶	(X)															
Letrozole ⁸	X-----X															
Everolimus ⁹	X-----X															
TRC105 ⁹		X	X	X	X	X	X	X	X	X	X	X	X	X	X	
Goserelin ¹³		X			X		X		X		X		X			
Surgery															X	

Notes:

1. Cholesterol, triglycerides, HDL, and LDL in a fasting state (8 hours) should be obtained at least on cycle 2 and, if elevated, repeat on each cycle until recovery to baseline value or grade 1.
2. Hepatitis panel should be obtained on screening and repeated as clinically indicated (HBV-DNA, HBsAg, HBs Ab, and HBc Ab, and RNA-PCR).

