8.2 Adverse reactions with everolimus

8.2.1 Clinical adverse reactions with everolimus

The most common ADRs (incidence $\geq 1/10$ and suspected to be related to treatment by the investigator) from the pooled safety data were (in decreasing order): stomatitis, rash, fatigue, diarrhea, infections, nausea, decreased appetite, anemia, dysgeusia, pneumonitis, hyperglycemia, weight decreased, pruritus, asthenia peripheral edema, hypercholesterolemia, epistaxis, and headache. The most common grade 3/4 ADRs (incidence $\geq 1/100$ to $< 1/10$ and suspected to be related to treatment by the investigator) were stomatitis, anemia, hyperglycemia, fatigue, infections, pneumonitis, diarrhea, asthenia, thrombocytopenia, neutropenia, dyspnea, lymphopenia, proteinuria, hemorrhage, hypophosphatemia, rash, hypertension, aspartate aminotransferase (AST) increased, alanine aminotransferase (ALT) increased, and pneumonia. **Table 8-1** presents the frequency category of ADRs reported in the pooled safety analysis.

Table 8-1: Adverse Drug Reactions associated with everolimus

Adverse Drug Reactions are listed according to MedDRA system organ class. Within each system organ class, the adverse reactions are ranked by frequency, with the most frequent reactions first. In addition, the corresponding frequency category using the following convention (CIOMS III) is also provided for each adverse reaction: very common ($\geq 1/10$); common ($\geq 1/100$ to $< 1/10$); uncommon ($\geq 1/1,000$ to $< 1/100$); rare ($\geq 1/10,000$ to $< 1/1,000$); very rare ($< 1/10,000$)	
Infections and infestations	
Very common	Infections ^a
Blood and lymphatic system disorders	
Very common Common Uncommon Rare	Anemia, Thrombocytopenia, neutropenia, leukopenia, lymphopenia Pancytopenia Pure red cell aplasia
Immune system disorders	
Uncommon	Hypersensitivity
Metabolism and nutrition disorders	
Very common	Decreased appetite, hyperglycemia, hypercholesterolemia
Common	Hypertriglyceridemia, hypophosphatemia, diabetes mellitus, hyperlipidemia, hypokalemia, dehydration
Psychiatric disorders	
Common	Insomnia
Nervous system disorders	
Very common	Dysgeusia, headache
Uncommon	Ageusia
Cardiac disorders	
Uncommon	Congestive cardiac failure
Vascular disorders	
Common	Hemorrhage ^b , hypertension,
Uncommon	Deep vein thrombosis
Respiratory, thoracic and mediastinal disorders	

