8.2.2 Clinically relevant laboratory abnormalities seen with everolimus

In the pooled double-blind phase III safety database, the following new or worsening clinically relevant laboratory abnormalities were reported with an incidence of $\geq 1/10$ (very common, listed in decreasing frequency).

- Hematology: hemoglobin decreased, lymphocytes decreased, white blood cells decreased, platelets decreased, and neutrophils decreased (or collectively as pancytopenia);
- Clinical chemistry: glucose (fasting) increased, cholesterol increased, triglycerides increased, AST increased, phosphate decreased, ALT increased, creatinine increased, and potassium decreased.

Most of the observed abnormalities ($\geq 1/100$) were mild (grade 1) or moderate (grade 2). Grade 3/4 hematology and chemistry abnormalities include:

- Hematology: lymphocytes decreased, hemoglobin decreased, (very common); neutrophils decreased, platelet count decreased, white blood cells decreased (all common).
- Clinical chemistry: glucose (fasting) increased, phosphate decreased, potassium decreased, AST increased, ALT increased, creatinine increased cholesterol (total) increased, triglycerides increased (all common).

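### Serum phosphate is in no scheduled chemistry panel, so hypophosphatemia, listed as a common grade 3/4 everolimus abnormality and not excepted from the DLT definition, is not systematically ascertained

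*Combined protocol and SAP*

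**What the plan says.** Three sections itemise the chemistry panel.

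- Screening (5.4.1): "serum chemistries (glucose, BUN, creatinine, total protein, albumin, bilirubin, calcium, alkaline phosphatase, AST, and ALT), serum electrolytes (Na, K, Cl), ferritin", followed by a fasting lipid panel.
- Treatment (5.4.2): "serum chemistries (glucose, BUN, creatinine, total protein, albumin, bilirubin, calcium, alkaline phosphatase, AST, and ALT), and serum electrolytes (Na, K, Cl) on week 1", repeated whenever a cycle starts, up to week 24.
- Early termination (5.4.3): the same ten chemistries, then "serum electrolytes (Na, K, Cl), and lipid panel (cholesterol, triglycerides, HDL, and LDL) in a fasting state (at least 8 hours".

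None of the three names phosphate, and none is worded as a list of examples. Table 7-1 has one generic row, "Chemistries/Electrolytes", and no footnote that adds an analyte.

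On expected toxicity, 8.2.2 gives the grade 3/4 clinical chemistry abnormalities as "glucose (fasting) increased, phosphate decreased, potassium decreased, AST increased, ALT increased, creatinine increased cholesterol (total) increased, triglycerides increased (all common"). Section 8.2.1 includes hypophosphatemia in its list of the most common grade 3/4 reactions: "lymphopenia, proteinuria, hemorrhage, hypophosphatemia, rash, hypertension". Section 5.2.2 also counts decreased phosphate among the most frequent laboratory abnormalities.

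The DLT definition in 4.1.1 opens with "Any grade 3 or 4 non-hematologic toxicity except anorexia, alopecia, nausea". The remaining exceptions in that item are fatigue and fever without neutropenia. Section 4.1.3 restricts DLTs for the MTD to the first cycle. The primary endpoint is the MTD, the RP2D and adverse-event rates (1.2.1), and 10.2 reports those rates with exact 95% intervals. Section 8.1 allows laboratory abnormalities to be adverse events.

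On glucose, 5.2.2.2 says: "Monitoring of fasting serum glucose is recommended prior to the start of Everolimus and periodically thereafter". Section 5.4.2 schedules glucose without a fasting condition; only the lipid panel must be fasting.

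**The concern.** The protocol names an abnormality as common at grade 3/4 and lets it count as dose-limiting, but does not schedule the test that would show it. A low phosphate without symptoms is a laboratory finding; without a scheduled measurement it appears only if someone orders the test for another reason. There is no baseline value to compare it with either.

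Two parts of the primary endpoint are affected. The adverse-event rate for hypophosphatemia would be estimated from patients most of whom were never tested, yet reported over the full denominator with an exact interval. And the 3+3 decision would usually be made without knowledge of laboratory-only phosphate events in cycle 1. Both errors make the combination look better tolerated than it may be.

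**Working it through.** **Coverage of the grade 3/4 chemistry list.** The eight abnormalities in 8.2.2, set against the scheduled panels:

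| Listed as common at grade 3/4 (8.2.2) | Where it is measured on treatment (5.4.2) |
|---|---|
| Glucose (fasting) | Chemistry panel; fasting not stated |
| Phosphate | Not scheduled |
| Potassium | Electrolytes |
| AST, ALT, creatinine | Chemistry panel |
| Cholesterol, triglycerides | Fasting lipid panel, at least on cycle 2 |

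Seven of the eight are measured. Phosphate is the only gap, which looks like an omission rather than a choice.

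**The plan's own figures.** No stated figure depends on phosphate, so there is none to reproduce on this point. As a check on method, 0.8^10 = 0.1074 agrees with section 10.1, and the Clopper-Pearson limits for 2, 4 and 6 of 20 agree within 0.1 percentage point.

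**What a zero count would look like.** If no event is recorded in 20 patients, the exact upper limit is 1 − 0.025^(1/20) = 16.8%, so the report would read 0% (0% to 16.8%). That interval assumes every patient was observed for the event, which the schedule does not provide.

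**How often there would be something to see.** Table 8-1 defines common as at least 1/100 and below 1/10. Taking a grade 3/4 rate q at the two ends of that band, P(at least one event) = 1 − (1 − q)^n:

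| n | q = 1% | q = 10% (limit of the band) |
|---|---|---|
| 3 | 3.0% | 27.1% |
| 6 | 5.9% | 46.9% |
| 20 | 18.2% | 87.8% |
| 38 | 31.7% | 98.2% |

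The rates come from pooled everolimus data and are not first-cycle rates. The rows therefore bear on the adverse-event analysis, not on the 3+3 decision.

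**Effect on the 3+3 rule.** Under Table 4-2 a level passes with 0 of 3 DLTs, or with 1 of 3 and then 0 of 3. With DLT probability p,

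pass(p) = (1 − p)^3 + 3p(1 − p)^2 × (1 − p)^3.

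Let b be the DLT probability from all other causes and q the cycle-1 probability of a laboratory-only grade 3/4 phosphate event, independent of the rest. If phosphate is unseen, p = b; if every such event is counted, p = 1 − (1 − b)(1 − q). Both b and q are assumptions. For b = 20%:

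- Unseen: p = 0.20, pass = 0.512 + 0.384 × 0.512 = 70.9%.
- q = 1%: p = 0.208, pass = 69.1%.
- q = 5%: p = 0.240, pass = 62.2%.
- q = 10%: p = 0.280, pass = 53.6%.

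The shift is about 2 to 17 percentage points. With b from 10% to 30% it runs from about 1 to 18 points. These differences compare complete detection with none.

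**The case against.** The strongest reply is that the event may be rare here and is not wholly invisible. Table 8-1 puts hypophosphatemia of any grade, as a drug reaction, in the common category (below 10%). Section 8.2.2 puts decreased phosphate of any grade at 10% or more, but as a laboratory abnormality in a phase III database. A drug-related grade 3/4 rate near 10% would sit badly with Table 8-1. In the closest setting, the neoadjuvant letrozole-everolimus trial summarised in 5.2.2 (137 patients), the most frequent biochemical grade 3/4 events run from hyperglycemia at 5.1% down to 1.5%, and phosphate is not among them. The documents do not say whether phosphate was measured in that trial, so this does not prove a low rate. It does make the upper end of the band unlikely, and that part of the reply stands.

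Three stronger readings are tempting, and the documents do not support them.

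- *Hypophosphatemia cannot be counted, or can never stop escalation.* An unscheduled or symptom-driven test would be recorded under 8.1 and could be a DLT under 4.1.1. The failure is of systematic ascertainment.
- *The 6% to 47% for six patients is the chance of a missed DLT.* It is not: 4.1.3 counts only the first cycle, and no first-cycle rate is given.
- *Hyperglycemia cannot be counted or graded reliably.* Glucose is in every scheduled chemistry panel, and 5.2.2.2 already recommends fasting values. Whether fasting status changes a grade 3/4 classification depends on CTCAE cut-offs that the protocol only links to. A blanket fasting requirement would also need reconciling with 6.1.3, which encourages water or juice before the first treatment.

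**Conclusion.** The point holds for phosphate. As written, hypophosphatemia is not systematically ascertained at screening, on treatment or at early termination. Its reported rate would be biased toward zero, and laboratory-only grade 3/4 events in cycle 1 would usually not reach the 3+3 rule.

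The direction is clear; the size is not. A grade 3/4 rate of 1% to below 10% is borrowed from the everolimus frequency category, and applying it to cycle 1 is a further assumption. The lower part of the band is more plausible than the upper. At 1% the effect on passing a dose level is under 2 points; at 5%, with 20% from other causes, it is about 9 points. The calculation also assumes independence.

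The glucose matter is secondary: a recommendation in 5.2.2.2 that was not carried into the schedule, leaving fasting and non-fasting values mixed.

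The change should be made. It concerns the primary safety endpoint, costs little, and values not obtained during treatment cannot reliably be recovered later.

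**What to change.** Add serum phosphate to the itemised panels in 5.4.1, 5.4.2 and 5.4.3, at the draws already scheduled, and name it in Table 7-1. If the sponsor prefers not to measure it, state in 10.2 that hypophosphatemia is not systematically assessed and report no rate or interval for it.

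For glucose, record fasting status at each draw, and reconcile 5.4.2 and Table 7-1 with the recommendation in 5.2.2.2.

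The cost is one routine analyte on existing draws and one extra data field. The adverse-event profile will look less favourable than an unmeasured one. Some isolated grade 3/4 phosphate values in cycle 1 will count as DLTs under 4.1.1 as it stands, which lowers the chance that a dose level passes, slightly at the low rates that seem most plausible. The sponsor should settle that consequence knowingly when the panel is amended; this review takes no position on what should be dose-limiting.
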